Adalimumab is not currently licenced for use as an intra-articular injection for people with pain-predominant early-stage frozen shoulder and will be used off license for the purposes of this trial. Therefore, as part of this feasibility trial we will also assess the safety of anti-TNF injection and record Adverse Events assessed by a clinician to be grade 3 or above as a result of the IMP injection.

Clinician assessed outcome:

- Shoulder range of movement.

[figure not shown]
Embedded qualitative sub-study (optional participation):

- To explore the patients' experiences of being recruited to a randomised trial of anti-TNF injection for frozen shoulder.
- To understand what helps or hinders participant recruitment to the trial intervention.

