The only means of accurately delivering the drug to the involved areas in patients with frozen shoulder is by ultrasound guidance. The skin at the site of injection of adalimumab/placebo will be infiltrated with the local anaesthetics to reduce the pain of the injection in accordance with local practice for an injection into the shoulder joint. Following administration of the local anaesthetic, there will be minimal discomfort associated with the intra-articular injection. Once adalimumab has been drawn up, it tends to lose its potency and this precludes preparation of the syringes before the patient presents for treatment. For this trial, no more than 30 minutes will elapse from when the injection is drawn up to when the injection is given.

The adalimumab/placebo will typically be delivered using a syringe fitted with typically a 21 gauge needle or greater. All participants irrespective of whether they are still in the pain predominant phase, will receive a second injection (adalimumab/placebo) administered 2-3 weeks after the first injection, unless the participant declines the second injection. The reason will be recorded on the trial specific injection treatment log and the participant will still be included in the 3-month follow up assessment. Participants will be advised to continue with their physiotherapy and resume normal activities immediately after the injection. Participants will be provided with a written information leaflet advising them that there will be no restriction on their activities after the injection and what to do if they experience any side effects. Each patient will receive a maximum of two injections, either adalimumab or placebo. Injection details, including time from randomisation to injection delivery, will be recorded on a trial specific injection treatment log. A second injection will not be administered if any related grade 3 or above Adverse Event as per the Common Terminology Criteria for Adverse Events (CTCAE) v5.0 occur following the first injection, or if the patient tests positive for TB or hepatitis B surface antigen.

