7.2. SAFETY REPORTING

7.2.1. Definitions

Adverse Event (AE)	Any untoward medical occurrence in a clinical trial participant administered a medicinal product and which does not necessarily have a causal relationship with this treatment.
Adverse Reaction (AR)	An untoward and unintended response in a participant to an investigational medicinal product that is related to any dose administered to that participant. The phrase “response to an investigational medicinal product” means that a causal relationship between a trial medication and an adverse event is at least a reasonable possibility, i.e., the relationship cannot be ruled out. All cases judged by either the reporting medically qualified professional or the sponsor as having a reasonable suspected causal relationship to the trial medication qualify as adverse reactions.
Serious Adverse Event (SAE)	An SAE is any untoward medical occurrence that: 1. results in death, 2. is life-threatening,

	
3. requires inpatient hospitalisation or prolongation of existing hospitalisation,
 
4. results in persistent or significant disability/incapacity, or
 
5. consists of a congenital anomaly or birth defect.
 
Other “important medical events” may also be considered serious if they jeopardise the participant or require an intervention to prevent one of the above consequences.
 
The term “life-threatening” in the definition of “serious” refers to an event in which the participant was at risk of death at the time of the event; it does not refer to an event which hypothetically might have caused death if it were more severe.

Serious Adverse Reaction (SAR)	An adverse event that is both serious and, in the opinion of the reporting investigator, is believed with reasonable probability to be due to one of the trial treatments, based on the information provided.
Suspected Unexpected Serious Adverse Reaction (SUSAR)	A serious adverse reaction, the nature and severity of which is not consistent with the information about the medicinal product in question set out in the summary of product characteristics (SmPC) for that product.

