7.2.2. Causality

The relationship of each adverse event to the trial medication must be determined by a medically qualified individual according to the following definitions:

Relationship to intervention	Attribution (causality)	Description
Unrelated	Unrelated	The AE is clearly NOT related to the intervention
	Unlikely	The AE is doubtfully related to the intervention
Related	Possible	The AE may be related to the intervention
	Probable	The AE is likely related to the intervention
	Definite	The AE is clearly related to the intervention

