7.2.3 Procedures for recording adverse events

The safety profile of adalimumab is well known, with the most common adverse reactions being mild injection site reactions. The Common Terminology Criteria for Adverse Events (CTCAE) v5.0 (will be used to guide recording Adverse Events including grading of the event. Only clinician assessed AEs, graded 3 and above, occurring during the trial for each participant, from their consent until the 3

month follow up and that are considered related to the IMP will be recorded on the CRF. Participants will be asked by the treating clinician at their 2nd injection visit if they have experienced any AEs as a result of their 1st injection. Similarly, participants will be asked if they have experienced any AEs as a result of their 2nd injection at the 3 month follow up appointment. Based on the information provided by the participant the treating clinician will then make an assessment as to whether it should be recorded as an AE grade 3 or above. The capture of all AEs in the trial CRFs is not deemed necessary due to the period of time for which the IMP has had a marketing authorisation and it's well established safety profile.

The following information will be recorded: adverse event term and grade, date of onset and end date, severity, assessment of relatedness to IMP/injection procedure, other suspect drug or device, action taken and outcome. Follow-up information should be provided as necessary. AEs considered related to the trial medication injection as judged by a medically qualified investigator will be followed either until resolution, or the event is considered stable. It will be left to the Investigator's clinical judgment to decide whether or not an AE is of sufficient severity to require the participant's removal from treatment. A participant may also voluntarily withdraw from treatment due to what he or she perceives as an intolerable AE. If either of these occurs, the participant must be given appropriate care under medical supervision until symptoms cease, or the condition becomes stable. Adverse events occurring as a result of the physiotherapy leaflet issued in the trial will not be recorded as part of the trial. The trial risk assessment identified no safety concerns, as advice and exercises given will be routine exercises that are used in standard care for this population. (16).

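### The only adverse event enquiry the protocol describes covers events the participant attributes to an injection; this is narrower than the protocol's own outcome, so some events may be missed

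*Combined protocol and SAP*

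**What the plan says.** Section 7.2.3 describes two enquiries. At the second-injection visit the treating clinician asks participants "if they have experienced any AEs as a result of their 1st injection". At 3 months the same is asked about the second injection only. The answer is what the clinician then works from in deciding whether there is a grade 3+ event to record: "Based on the information provided by the participant the treating clinician will then make an assessment". Only grade 3+ events that are considered related to the trial product go on the CRF.

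Other sections bear on this:

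- Section 7.2.1 defines an adverse event as an occurrence "which does not necessarily have a causal relationship with this treatment".
- Section 7.2.2 states: "The relationship of each adverse event to the trial medication must be determined by a medically qualified individual". It uses a five-level scale on which Possible already counts as related.
- Table 2 (section 4.4.2) and Table 3 (section 6.1.1) define the outcome as every grade 3+ event from consent to 3 months, with no relatedness condition.
- The timeline in section 4.5 and the schedule in Appendix 2 list grade 3+ event reporting or assessment at screening, at both injection visits and at 3 months. They give no method of asking.
- Section 4.3.1 states: "A second injection will not be administered if any related grade 3 or above Adverse Event" follows the first injection.
- Section 3.2 says that "we will also assess the safety of anti-TNF injection". The same sentence confines recording to grade 3+ events that a clinician judges to result from the injection.

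**The concern.** The enquiry puts a lay judgement of cause ahead of the medical one. It also sets a stricter test: the participant must believe that the injection caused the event, whereas section 7.2.2 classes an event as related if it merely may be. An event that a doctor would call Possible can drop out before any doctor hears of it.

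The loss is unlikely to be even across event types. A painful shoulder after a shoulder injection will be mentioned. A chest or urinary infection some weeks later may not be. Yet section 4.3.1 expects absorption into the blood much as after subcutaneous dosing, and section 4.2.2 excludes people with active or recurring infection, so the protocol itself treats non-local effects as relevant.

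Two uses of the data are exposed. One is the safety summary by group in section 6.3, which would inform planning of the definitive trial. The other is the section 4.3.1 rule on the second injection, which can be applied only to what is known at that visit.

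**Working it through.** **1. The sections side by side**

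| Place | Events covered | Who judges cause |
|---|---|---|
| 7.2.1 | any, causal or not | not applicable |
| 7.2.2 | each adverse event | medically qualified person |
| Tables 2 and 3 | all grade 3+ from consent | no condition |
| 4.5 and Appendix 2 | grade 3+, four time points | no condition |
| 7.2.3, questions | those the participant attributes to the stated injection | participant, in choosing what to mention |
| 7.2.3, CRF | grade 3+ and related | clinician |

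The question row is the narrowest entry point, and it comes before the clinician's row.

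**2. Coverage of the two questions**

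The visit-2 question covers the first injection and the 3-month question covers the second. An event that follows the first injection but arises after visit 2 falls under neither. Nor does any event in a participant who did not have the second injection and so had no second-injection visit, although section 4.3.1 keeps such participants in the 3-month follow-up.

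**3. Other ways in**

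- An event may be volunteered.
- A related SAE must be reported once the site knows of it (section 7.2.4), but only up to 28 days after the last injection. With the second injection at 4 to 5 weeks (section 4.5), that window ends at 4 + 4 = 8 to 5 + 4 = 9 weeks. The 3-month visit is at about 13 weeks, so roughly 4 to 5 weeks lie outside it.
- An investigator may act on any event that becomes known (sections 6.1.3 and 7.2.3).

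None of these is a planned enquiry.

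**4. Illustration of size**

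The plan gives no figure for this point. Inputs:

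- n = 42 given adalimumab: 84 randomised 1:1 (section 5.5), 84/2 = 42, assuming all are injected.
- p, the true risk of a related grade 3+ event: assumed.
- s, the share of such events that the question brings out: assumed.

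Chance of recording none = (1 − p·s)^42.

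| | s = 100% | s = 75% | s = 50% | s = 25% |
|---|---|---|---|---|
| p = 5% | 0.95^42 = 12% | 0.9625^42 = 20% | 0.975^42 = 35% | 0.9875^42 = 59% |
| p = 2% | 0.98^42 = 43% | 0.985^42 = 53% | 0.99^42 = 66% | 0.995^42 = 81% |

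If none of 42 has a recorded event, the one-sided 95% upper bound on the recorded rate is 1 − 0.05^(1/42) = 6.9%. Dividing by s gives the bound on the true rate: 6.9% at s = 100%, 9.2% at 75%, 13.8% at 50% and 27.5% at 25%.

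**The case against.** The strongest defence is that the limited scope is deliberate. Section 7.2.3 argues that the product's established safety profile makes full capture unnecessary, and the aim in section 3.2 is itself limited to events that a clinician ties to the injection. That is a fair reason to record less. It does not justify letting the participant make the first cut, because both sections give attribution to a clinician.

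A reader might infer more: that unlinked events can never be elicited or reach the second-injection rule, and that the participant decides causality. The documents do not support this. Tables 2 and 3 and both schedules call for grade 3+ events without an attribution limit. Related SAEs are reportable however they come to light. Participants receive a leaflet on side effects (section 4.3.1) and a card with site contact details (section 5.4). The section 4.3.1 rule is not confined to events raised by the question, and the recorded causality decision stays with a medically qualified person. The participant filters what is raised and no more.

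Two further objections stand as limits. Section 7.2.3 reports the questions indirectly and the CRF is not among the documents, so the prompt used at sites may be better than the text. The illustration also applies one s to all related events, whereas local reactions would mostly be mentioned; the overall s depends on a local/systemic mix that is not given. If events are as rare as section 7.2.4 expects, a zero count is likely either way: at p = 1% the chance is 66% with s = 100% and 81% with s = 50%.

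**Conclusion.** The concern holds in a limited form. The one enquiry that the protocol describes is restricted to events the participant links to a particular injection. That is narrower than the outcome in Tables 2 and 3 and the visit schedules, and it precedes the assessment reserved for a medically qualified person. Other events depend on being volunteered or on another route, so they may be missed in the safety summary and when the second-injection rule is applied. Late events after the first injection, and participants without a second one, have no described enquiry.

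The conflict between sections rests on the text alone. The size does not: both p and s are assumed, and 42 is a maximum, since section 4.3.1 allows for participants who are not injected. What the figures show is that a zero count in this trial would be weaker reassurance than it appears. The point merits a change because the remedy is cheap.

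**What to change.** In section 7.2.3, replace both questions with a neutral one that covers the whole period since the last contact, for example whether the participant has had any new or worse health problem, medical visit or new medicine. Put it to every participant seen at the existing second-injection and 3-month visits, whether or not a second injection was given. Have the medically qualified assessor assign relatedness afterwards under section 7.2.2. Check that the CRF prompt carries the same wording.

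Then reconcile section 7.2.3 with Tables 2 and 3, the section 4.5 timeline and Appendix 2, so that all state whether the outcome is any grade 3+ event or only related ones. Restricting the CRF to related events can be kept if that is the intention, provided the tables say so.

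No change to the second-injection rule is proposed. No visit is added. The cost is an amendment to the text and prompt, and a few more unrelated mentions for the clinician to triage.

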7.2.4. Reporting procedure for serious adverse events

SAEs occurring to a participant, from the time of their consent up to 28 days after their last injection of trial treatment, must be reported to the Trial Office. Only SAEs that are related to trial medication (adalimumab/placebo) or the injection of the trial medication are required to be reported to the trial office. The reporting to the trial team of SAEs not related to the IMP/injection is deemed not necessary. Causality (relatedness) must be assessed by a medically qualified doctor.

SAEs must be recorded on the trial specific SAE form electronically via REDCap. The SAE must be reported immediately (within a very short period of time and under no circumstances should this exceed 24 hours following knowledge of the SAE) following the Site Study Team becoming aware of the event. Alternatively, a paper SAE form can be completed and must be submitted to the Trial Office via email:

Trial Office contact: [contact]

The Trial Office will review the information on the SAE and raise immediate queries for any key data which is missing. In the event where the reporting site does not provide an assessment of causality the Trial Office will assume that the event is related to the IMP. The SAE form will also be reviewed by a Nominated Person, as per OCTRU SOPs for safety reporting, who will provide an assessment of expectedness in line with the reference safety information for the IMP(s). The SAE form will also be reviewed by the Chief Investigator. In the event where any representative of the Sponsor (CI/Trial team/Nominated Person) disagrees with the assessment of the site PI, a discussion will be encouraged between the two to re-assess the event. If either the PI or the representative of the Sponsor continue to assess the event as related, both assessments will be recorded, and the event will be considered as related. If the event is both related and unexpected this will be reported as a SUSAR by the Trial Office or delegate to the relevant Competent Authorities, UK Ethics, Sponsor and other bodies in which the national and local regulations of participating sites require, as per 7.2.5 below. All related SAEs will be followed till resolved or no further information is expected. SAEs will only be considered closed when signed off by the local PI. For this study, adverse events and serious adverse events are likely to be rare. If they occur, they will be reviewed by the Trial Management Group.

The reference safety information (RSI) will be section 4.8 of the Summary of Product Characteristics (SmPC) for both Adalimumab and placebo. The RSI used will be the current Sponsor and MHRA approved version at the time of the event occurrence. The SmPC to be used as the RSI will be specified in the MHRA applications.

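### Sites must report only the SAEs they already judge related, so the sponsor's own say on causality has little to act on where it matters for SUSAR detection

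*Combined protocol and SAP*

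**What the plan says.** Section 7.2.4 opens broadly: "SAEs occurring to a participant, from the time of their consent up to 28 days after their last injection of trial treatment, must be reported". The next sentence narrows this: "Only SAEs that are related to trial medication (adalimumab/placebo) or the injection of the trial medication are required to be reported to the trial office". A third removes the remainder: "The reporting to the trial team of SAEs not related to the IMP/injection is deemed not necessary". On who decides, it says only: "Causality (relatedness) must be assessed by a medically qualified doctor".

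The same section then describes central review. The Trial Office, a Nominated Person (for expectedness) and the Chief Investigator look at each form received. On disagreement: "If either the PI or the representative of the Sponsor continue to assess the event as related, both assessments will be recorded". Such an event then counts as related. There is also a default: "In the event where the reporting site does not provide an assessment of causality the Trial Office will assume that the event is related".

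The definitions in section 7.2.1 are not uniform. An adverse reaction includes "All cases judged by either the reporting medically qualified professional or the sponsor as having a reasonable suspected causal relationship", so either party's view suffices. A serious adverse reaction is one that, "in the opinion of the reporting investigator, is believed with reasonable probability to be due to one of the trial treatments", which names one party and sets what reads as a higher threshold. Section 7.2.2 places 'Possible' under Related and 'Unlikely' under Unrelated.

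Section 7.2.3 restricts the AE CRF to grade 3 or higher events considered related to the IMP. Tables 2 and 3 list any AE of grade 3 or above, with no condition on relatedness. Section 6.3 promises AEs and SAEs summarised per group and overall.

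**The concern.** An either-party rule exists mainly to catch the serious event that a site calls unrelated and the sponsor would call related. Here the site's judgement is applied before the report is made, so for that event the sponsor need never receive a form. Events rated 'Unlikely', where a second opinion is most useful, fall on the unreported side.

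This matters more than usual because sections 3.1.3 and 3.2 say that intra-articular use is unlicensed in this condition and that the trial will for that reason assess safety. The oversight committee in section 9.2.3, which advises on whether the trial should continue, can count on seeing only the filtered events. A summary by arm confined to events judged related depends on attribution. A count of all SAEs by arm does not, and under the present wording it is not assured.

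**Working it through.** The plan gives no figure on this point, so there is nothing to reproduce. The check is to follow each combination of opinions through section 7.2.4.

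**Paths through the reporting rule**

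1. Site says related and the PI keeps that view: the event is related whatever the sponsor thinks. The sponsor's view changes nothing.
2. Site says related and the PI later moves to unrelated: the event is related if the sponsor holds it related, and unrelated if the sponsor agrees with the PI. The sponsor's view decides.
3. Site sends a report with no causality opinion: related by default. The sponsor's view changes nothing.
4. Site says unrelated and the sponsor would say related: related under the either-party rule, but no report is required, so the rule has no assured input.
5. Site says unrelated and the sponsor would agree: unrelated, and no report is required.

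Among reports that must be made, the sponsor's opinion alters the result only in path 2. Path 4, the upgrade, is open only if a site volunteers the report.

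**Is there a second route to the sponsor?** The AE CRF would be the obvious one. Section 7.2.3 applies the same relatedness filter to it. Tables 2 and 3 do not, so the documents conflict and this route cannot be relied on to recover path 4.

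**Definitions.** Take a reported, unexpected SAE that is rated 'Possible', or that only the sponsor thinks related.
- Under section 7.2.4, an event that is related by either party's view and unexpected is reported as a SUSAR.
- Under section 7.2.1, a SUSAR must first be a serious adverse reaction, which needs the reporting investigator's belief to a reasonable probability. Section 7.2.5 reports SAEs that meet that definition. On this route the event arguably does not qualify.

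The two routes should give the same answer.

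**Illustration of what the second opinion is worth.** Let s be the chance that the site recognises a truly related SAE, and t the chance that the sponsor does, taken as independent. Ignore voluntary reports and missing opinions. The documents give neither value, so both are assumptions.
- Site filter alone: s.
- Either-party rule with all SAEs reported: 1 − (1 − s)(1 − t).
- s = t = 0.70: 1 − 0.30 × 0.30 = 0.91, against 0.70.
- s = t = 0.95: 1 − 0.05 × 0.05 = 0.9975, against 0.95.

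If the two opinions tend to agree, the gain is smaller.

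**Workload.** The documents give no SAE rate. Assuming 2–5% of the 84 participants have an SAE in the window:
- 84 × 0.02 = 1.7
- 84 × 0.05 = 4.2

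That is about 2 to 4 SAEs of any cause. Related ones are already reported, so the extra forms number at most this.

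**The case against.** Several points on the other side are sound.

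- **The rule is not dead.** A reader might infer that the sponsor's opinion can never change a classification. The documents do not support that. Unrelated SAEs are not required, but they are not barred. The doctor who judged the event related may not be the PI, and if the PI disagrees or later changes view, the sponsor's opinion decides. Missing causality defaults to related.
- **SUSAR classification does not rest wholly on one site opinion.** A reader might infer that too. For a reported event, expectedness is judged centrally, and section 7.2.4 already makes any event that is related by either view and unexpected a SUSAR. The narrower SAR definition is therefore a wording conflict to tidy. It is not shown to lose SUSARs.
- **The site threshold is low.** An event that may be related, to the drug or to the injection itself, counts as related. A serious infection drops out only if a doctor rates it unlikely or clearly unrelated.
- **Selective capture is a reasoned choice.** Section 7.2.3 justifies it by the marketing authorisation and known safety profile. That argument is written for AEs, however, and it sits uneasily with the protocol's own statement that this route is unlicensed and is to be assessed for safety.
- **The numbers are small.** With a handful of SAEs, a comparison by arm will say little.

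All of this limits how strongly the point can be put. None of it gives the sponsor required sight of an SAE the site has called unrelated.

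**Conclusion.** The point holds in a limited form. Section 7.2.4 filters on site causality before sponsor review, so the either-party rule is largely ineffective in the one direction that could add a SUSAR. The SAE summary in section 6.3 is assured only for events judged related at site.

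The conclusion rests on the wording alone and needs no assumption about event rates. Its practical size cannot be derived from the documents, which say only that such events are likely to be rare. The recognition probabilities and the 2–5% rate above are assumptions. The change is worth making because it is cheap, resolves an internal contradiction and removes attribution from the basic SAE count. It would not make an 84-participant feasibility study informative about differences in SAE rates.

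**What to change.** 1. In section 7.2.4, replace the two sentences that confine reporting to related SAEs with a requirement to report every SAE in the existing window (consent to 28 days after the last injection), together with the site's causality opinion.
2. State that the sponsor records its own causality assessment for each SAE and that SUSAR status follows from either opinion, as section 7.2.4 already intends.
3. In section 7.2.1, define a serious adverse reaction as an adverse reaction, as already defined there, that is serious. This carries over the either-party test and the reasonable-possibility threshold, and brings section 7.2.5 into line with section 7.2.4.
4. Reconcile Tables 2 and 3 (any AE of grade 3 or above) with section 7.2.3 (related only), so that sites have one recording rule.
5. In section 6.3, specify two descriptive tables by arm for the SAE window: all SAEs and related SAEs. Because the window is tied to the last injection, label them as covering that window and not the whole 3-month follow-up.

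The cost is an amendment to protocol wording and a small extra workload at sites: at most about 2 to 4 additional forms across the trial on the assumed rate.
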